14.2 Terminology for classification of SAEs

A simple and brief description of **clinical symptoms** should be given using the following descriptions to record information about AEs:

1. Severity will be described using the following categories:

- **Mild**—the adverse event does not interfere with the volunteer’s daily routine, and does not require intervention; it causes slight discomfort.
- **Moderate**—the adverse event interferes with some aspects of the volunteer’s routine, or requires intervention, but is not damaging to health; it causes moderate discomfort.
- **Severe**—the adverse event results in alteration, discomfort or disability which is clearly damaging to health.

2. Relationship to treatment — the assessment of relationship of AEs to the administration of IMP is a clinical decision based on all available information at the time of the completion of the CRF. The following categories will be used:

- **Definitely** — there is clear evidence to suggest a causal relationship, and other possible contributing factors can be ruled out.
- **Probably** — there is evidence to suggest a causal relationship, and the influence of other factors is unlikely.
- **Possibly** — there is some evidence to suggest a causal relationship (e.g. the event occurred within a reasonable time after administration of the trial medication). However, the influence of other factors may have contributed to the event (i.e. the patient’s clinical condition, other concomitant events).
- **Unlikely** — there is little evidence to suggest there is a causal relationship (e.g. the event did not occur within a reasonable time after administration of the trial medication). There is another reasonable explanation for the event (*e.g.* the patient’s clinical condition, other concomitant treatments).
- **Not related** — there is no evidence of any causal relationship.
- **Not Assessable**

3. Expectedness will be described using following categories:

- **Expected** — an AE that is classed in nature as serious and which is consistent with the information about the IMP listed in the Investigator Brochure (or SmPC) **or clearly defined in this protocol.**
- **Unexpected** — an AE that is classed in nature as serious and which is not consistent with the information about the IMP listed in the Investigator Brochure (or SmPC).

14.3 Recording of Safety Information

Collection, recording and reporting of AEs (including serious and non-serious events and reactions) to the Sponsor will be done according to the Sponsor’s Pharmacovigilance SOP.

14.3.1 Adverse Events (AEs)

All Adverse Events will be recorded in the hospital notes in the first instance.

A record of all AEs, whether related or unrelated to the treatment will also be kept in the CRF.

If the Investigator suspects that the disease has progressed faster due to the administration of the IMP, then he/she will report this as an unexpected adverse event to the sponsor.

14.3.2 Serious Adverse Events (SAEs)

All SAEs will be recorded in the hospital notes and the eCRF.

All SAEs will be reported to the Sponsor *via* the Inform System on an SAE form unless otherwise stated in the protocol. The Chief or Principal Investigator will complete the Inform SAE reporting form and the form will be faxed to the RO on [name] or E-mailed to [contact], *via* Inform system within 24hrs of the Investigator becoming aware of the event.

The Chief or Principal Investigator (CI/PI) will respond to any SAE queries raised by the Sponsor as soon as possible.

Medical oxygen is licensed in the UK and will be used within its marketing authorization in this study. The most up to date version of the SmPC will be used as the IMP reference document for this study.

14.3.3 Specific Adverse Events to be captured

At each visit patients will undertake study related assessment to check for adverse events. The data manager will perform regular checks which will be reviewed by the CI and DMC reports, on the eCRF and produce reports where the following parameters have exceeded an acceptable value.

Specific AE's that require recording on the eCRF include:

- Chest infections
- Headache(s)
- Disease Progression Expected SAE/Rs

14.3.4 Expected SAE/Rs related to IMP

Expected Adverse Reactions are known side effects of the IMP reported in SmPCs of Medicinal Oxygen.

Ambulatory oxygen therapy is usually associated with only mild side effects, which may include nasal mucosa dryness or skin irritation from the nasal cannula.

14.3.5 Expected SAEs related to underlying disease

Events that are expected and related to underlying disease include study endpoints, disease progression, chest infections and death secondary to disease progression.

14.4 Reporting Adverse Events (AEs) – (including SAE/Rs)

- a) There is routine monitoring of patient status, blood tests and lung function and data will be captured on the eCRF.
- b) All SAEs/SARs (including expected) will be recorded on the eCRF by the investigator/or designee within 24 hours of their becoming aware of the event. The eCRF will send a notification of each SAE report to the Research Office (*via* email detailed in section 15.3.2) and the CI (or designee) who will review the report within 2 working days of receipt.
- c) Prolongation of hospital admission or new hospital admission for infections which are related to IMP and or the underlying disease progression investigators are required to report within 7 days of their becoming aware of the event.
- d) All SAEs, whether related or unrelated to the treatment will be recorded in the hospital notes and eCRF. The Sponsor will have access to SAEs *via* the eCRF.
- e) If the Investigator suspects that the disease has progressed faster due to the administration of the IMP, then s/he will report this as an unexpected AE.

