14.1 Definitions

Adverse Event (AE) — any untoward medical occurrence in a patient or clinical trial subject who is administered an IMP and which does not necessarily have a causal relationship with this treatment. (*i.e.* any unfavourable or unintended change in the structure (signs), function (symptoms), or chemistry (lab data) in a subject to whom an IMP has been administered, including occurrences unrelated to that product)

Adverse Reaction (AR) — any untoward and unintended responses to an IMP related to any dose administered (*i.e.* any unfavourable or unintended change in the structure (signs), function (symptoms), or chemistry (lab data) in a subject to whom an IMP has been administered and related to any dose administered)

Serious Adverse Event (SAE) or Serious Adverse Reaction (SAR)—any Adverse Event or Reaction in a trial subject that:

- Results in death; or
- Is life-threatening (places the subject, in the view of the Investigator, at immediate risk of death)
- Requires hospitalisation or prolongation of existing hospitalisation (hospitalisation is defined as an inpatient admission, regardless of length of stay; even if it is a precautionary measure for observation; including hospitalisation for an elective procedure, for a pre-existing condition)
- Results in persistent or significant disability or incapacity (substantial disruption of one's ability to conduct normal life functions)
- Consists of a congenital anomaly or birth defect (in offspring of subjects or their parents taking the IMP regardless of time of diagnosis).

Important medical events that may not be immediately life-threatening or result in death or hospitalisation but may jeopardise the subject or may require intervention to prevent one of the outcomes listed in the definition of serious will also be considered serious.

Suspected Unexpected Serious Adverse Reaction (SUSAR) — an Adverse Reaction which is classed in nature as both serious and unexpected.

An Unexpected Adverse Reaction is an Adverse Reaction, when both the nature and severity of the event is not consistent with the information about the medicinal product in question, as set out below:

- (a) in the case of a product with a marketing authorization, in the Summary of Product Characteristics (SmPC) for that product,
- (b) in the case of any other IMP, in the Investigator's Brochure relating to the trial in question.

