14.4.1 SUSARs

All SUSARs will be notified to the Sponsor immediately or at least within 24hrs of the Investigator becoming aware of the event. Investigators must complete the appropriate SAE form on the eCRF and an automatic email notification will be sent to the Research Office and the CI immediately. The Research Office on behalf of the Sponsor will ensure that the report is reviewed by the CI (or designee) within 2 days to ensure it constitutes a SUSAR and requires expedited reporting by the Research Office.

All SUSAR will be disseminated to study PIs and participating sites *via* the research team at RBH.

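### Section 14.4 gives the same infection-related hospital admissions two reporting deadlines, 24 hours in item (b) and 7 days in item (c), and item (c) includes admissions related to the IMP

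*Protocol*

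**What the plan says.** All references are to the Protocol.

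- **Seriousness (14.1).** An event is serious if, among other criteria, it "Requires hospitalisation or prolongation of existing hospitalisation".
- **General SAE rule (14.3.2).** SAEs go to the sponsor "within 24hrs of the Investigator becoming aware of the event". This section also carries a proviso that allows the protocol to state otherwise.
- **Item 14.4(b).** The rule reads: "All SAEs/SARs (including expected) will be recorded on the eCRF by the investigator/or designee within 24 hours of their becoming aware". That entry then triggers a notification to the Research Office and the CI. No exception is given.
- **Item 14.4(c).** The events covered are given as "Prolongation of hospital admission or new hospital admission for infections which are related to IMP and or the underlying disease progression". The limit set for this group is a week: "investigators are required to report within 7 days of their becoming aware of the event".
- **SUSARs (14.4.1).** "All SUSARs will be notified to the Sponsor immediately or at least within 24hrs", again with no exception.
- **Expectedness.** Section 14.3.5 reads "Events that are expected and related to underlying disease include study endpoints, disease progression, chest infections", and adds death from progression. For the IMP, section 14.3.4 refers to the SmPC and itself names only nasal dryness and skin irritation from the cannula.
- **Deaths (14.5).** All deaths, related or not, go to the CI and the sponsor within 24 hours of the PI becoming aware.
- **Regulator (14.6).** For fatal or life-threatening SUSARs the limit is 7 calendar days from the Research Office's receipt of the SAE form. For other SUSARs it is 15 calendar days from the Research Office's first knowledge of the minimum criteria for expedited reporting.

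**The concern.** Items (b) and (c) are consecutive entries in one list, and every event that meets (c) also meets (b). A site that admits a patient with an infection therefore reads two deadlines for one report, and nothing in section 14.4 says which prevails.

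The wording of (c) makes this more than untidy. It is not limited to expected infections due to the underlying disease: it expressly includes infections related to the IMP. Those are SARs, and the sponsor must review them promptly to decide whether they are unexpected. The decision on whether an event is a SUSAR is confirmed by the CI after the site has reported it, so a late site report delays that decision and the regulatory steps that follow.

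The protocol itself anticipates this kind of event. Chest infections are a specific AE to be captured in section 14.3.3 and an expected SAE of the underlying disease in section 14.3.5.

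**Working it through.** The protocol gives no figure to reproduce here. The check compares the rules and then does the date arithmetic.

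**Step 1. Which rules apply to an infection admission?**

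| Event | 14.4(b) | 14.4(c) | Other rule |
|---|---|---|---|
| Related to disease progression only | 24 hours | 7 days | 14.3.2: 24 hours, with proviso |
| Related to IMP, expected (SAR) | 24 hours | 7 days | 14.3.2: 24 hours, with proviso |
| Related to IMP, unexpected (SUSAR) | 24 hours | 7 days | 14.4.1: 24 hours |
| Any of the above, once fatal | 24 hours | 7 days for the admission | 14.5: 24 hours for the death |

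In each of the first three rows, (b) and (c) disagree.

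**Step 2. Does the proviso in 14.3.2 settle it?** It qualifies only 14.3.2. It could make (c) a deliberate departure from that section. It does not qualify 14.4(b), which covers all SAEs and SARs and expressly includes expected ones, or 14.4.1, which covers all SUSARs.

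**Step 3. Can an event under (c) be a SUSAR?** It must be IMP-related, which (c) allows, and unexpected. The protocol lists chest infections as expected only in relation to the underlying disease, and it names no infection among the reactions to oxygen. The reference document is the SmPC, which is not available here. The event is therefore a possible SUSAR and no more than that.

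**Step 4. Size of the gap.** Take 24 hours as 1 day.

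- Extra time at site level: 7 − 1 = 6 days at most.
- Longest time from site awareness to regulator = site deadline + Research Office deadline.
- Life-threatening, non-fatal SUSAR: 7 + 7 = 14 days under (c), against 1 + 7 = 8 days under (b) or 14.4.1.
- Other SUSARs: 7 + 15 = 22 days, against 1 + 15 = 16 days.

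The second and third sums assume that every party uses its full allowance. The third also assumes that the Research Office first learns of the minimum criteria when the site reports. The CI review period (2 working days in 14.4(b), 2 days in 14.4.1) is not added. For the 7-day limit it runs inside the clock, which starts at receipt; for the 15-day limit this follows from the same assumption.

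**The case against.** The strongest reply is that a site can satisfy every rule at once. Recording the event on the eCRF within 24 hours meets (b), (c), 14.3.2 and 14.4.1 together, so (c) would be only a looser, redundant limit. One could add that (b) governs recording while (c) governs reporting. It is true that a site following (b) causes no delay. But under (b) the eCRF entry is itself the notification, so the recording/reporting distinction leaves (c) with nothing to do. If (c) has a function, it is to relax (b). On either reading the text needs correcting.

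A second reply is that (c) is an intended exception under the proviso in 14.3.2. For infections related only to disease progression this is plausible as regards 14.3.2. It fails for (b), which has no proviso, and it gives no reason for including IMP-related infections.

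Other points on that side do stand, and they rule out stronger readings that a reader might infer:

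- **That SUSARs will routinely arrive six days late.** Section 14.4.1 separately requires all of them within 24 hours. The delay needs a site to apply (c) instead, or not to have recognised the event as a SUSAR.
- **That a fatal SUSAR could reach the regulator after 14 days.** Section 14.5 keeps every death at 24 hours.
- **That 22 days is the expected time for other SUSARs.** The 15-day clock runs from first knowledge of the minimum criteria, and 14.4(d) gives the sponsor access to SAEs through the eCRF, so the clock can start earlier.
- **That infection admissions are a main class of safety report here.** No rate is given. The trial plans 80 patients, each free of chest infection for the four weeks before randomisation and each with two weeks on oxygen. Section 12 expects no oxygen toxicity. IMP-related, unexpected infection admissions are likely to be few.

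**Conclusion.** The point holds as an internal contradiction in a safety-reporting rule. Section 14.4(c) conflicts with 14.4(b) for every event it covers, and with 14.4.1 for any of those events that is a SUSAR.

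The consequence is conditional. If a site works to (c), or has not yet seen that the event is a SUSAR, an IMP-related infection admission can reach the sponsor up to 6 days later than (b) requires. The regulator figures (14 against 8 days for life-threatening, non-fatal SUSARs; 22 against 16 days for others) are outer bounds and apply only if the event proves to be a SUSAR, which depends on the SmPC. The conflict between (b) and (c) does not depend on that: an IMP-related infection admission is an SAR, and so falls under (b), whether or not it is expected.

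Few patients are likely to be affected, and no endpoint or analysis is touched. The text is still wrong as written and should be corrected, because it offers sites a longer deadline for events that the same section requires within 24 hours.

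**What to change.** Reconcile sections 14.3.2, 14.4(b), 14.4(c) and 14.4.1 so that each class of event has one reporting deadline.

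- At minimum, take IMP-related events out of 14.4(c), so that no SAR or possible SUSAR falls under two deadlines.
- If the sponsor wants to keep (c) for infections related only to the underlying disease, state it in 14.4(b) as an explicit exception and refer to it from 14.3.2.
- Otherwise delete (c).

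The cost is a short text amendment and a note to the three sites. Some infection admissions may be reported sooner. Treatment, assessments, endpoints and sample size are unchanged.

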14.4.1 SUSARs

All SUSARs will be notified to the Sponsor immediately or at least within 24hrs of the Investigator becoming aware of the event. Investigators must complete the appropriate SAE form on the eCRF and an automatic email notification will be sent to the Research Office and the CI immediately. The Research Office on behalf of the Sponsor will ensure that the report is reviewed by the CI (or designee) within 2 days to ensure it constitutes a SUSAR and requires expedited reporting by the Research Office.

All SUSAR will be disseminated to study PIs and participating sites *via* the research team at RBH.

14.5 Notification of deaths

We do not expect any deaths to occur as a consequence of ambulatory oxygen. However, all deaths, including deaths unrelated to the IMP, even if they occur earlier than expected, will be reported to the CI and the study Sponsor within 24 hours of the PI becoming aware.

14.6 Reporting to Regulatory Authority

The RO will notify all SUSARs to the MHRA electronically *via* e-SUSARs Database and the main REC using the CIOMS form. The CIOMS form should be completed by the CI and PI at each site and sent to the RO as described in Section 15.3.2 of the protocol.

The RO will inform the MHRA and the main REC of fatal or life threatening SUSARs as soon as possible, but no later than 7 calendar days after the RO receives the SAE report form. Any additional information will be reported within 8 days of sending the first report.

The RO must report all other SUSARs and safety issues to the MHRA and main REC, as soon as possible but no later than 15 calendar days after the RO has first knowledge of the minimum criteria for expediting reporting.

14.7 The type and duration of the follow-up of subjects after AEs

Any SUSAR related to the IMP will need to be reported to the Sponsor irrespective of how long after IMP administration the reaction has occurred.

14.8 Development Safety Update Reports

The CI or a delegated PI will prepare the DSUR, using the Sponsor's DSUR template and in accordance with the Sponsor's DSUR SOP. It will be reviewed by the Sponsor and when necessary be referred to an independent committee (*i.e.* Clinical Trials Oversight Committee (CTOC)). The RO will provide the main REC and the MHRA with a copy of the study DSUR.

14.9 Annual Progress Reports (APRs)

The Chief Investigator will prepare the APR. It will be reviewed by the JRO and sent to the main REC within 30 days of the anniversary date on which the favourable opinion was given by the Ethics committee, and annually until the trial is declared ended.

14.10 Pregnancy

There are no known side effects and/or harmful effects of ambulatory oxygen during pregnancy. In the unlikely event of a pregnancy occurring during the 4 week trial period while patients are receiving treatment as part of the study (IPF and other idiopathic fibrotic lung diseases are more common in older age groups and in males), the pregnant patient will not be removed from the trial. If the discovery of the pregnancy were to fall within the two weeks of no ambulatory oxygen the patient would be advised to continue with the prescribed ambulatory oxygen, to avoid hypoxia to the foetus.

As oxygen is not a drug, follow up of the mother and child would follow standard of care, and there would be no need for follow up specific to the ambulatory oxygen. However, as part of routine clinical care of a pregnant patient with significant lung fibrosis and gas exchange abnormalities, the patient would be referred to a centre with expertise in management of pregnancies in the context of significant lung disease, and she would remain under close follow up of the Interstitial Lung Disease Unit (ILDU) in the relevant centre, in the period up to and following delivery of the baby.

Despite ambulatory oxygen being beneficial during pregnancy, all pregnancies will be reported to the study Sponsor as described in Sponsor's PVG SOP. Patients will be excluded from the study but will be invited to attend future study visits. The specialist ILDU will be asked to provide follow up information to the CI regularly and on request until the delivery of the baby.

14.11 Reporting Urgent Safety Measures

Regulation 30 of the Medicines for Human Use (Clinical Trials) Regulations 2004 [Statutory Instrument 2004/1031], as amended by Statutory Instrument 2006/1928 states “the Sponsor and the Investigator may take appropriate urgent safety measures in order to protect the subjects of a clinical trial against any immediate hazard to their health or safety. If measures are taken, the Sponsor shall immediately and in any event no later than 3 days from the date the measures are taken, give written notice to the MHRA and the relevant REC of the measures taken and the circumstances giving rise to those measures.”

In order to prevent any delays in the reporting timelines the Sponsor has delegated this responsibility to the CI/PI. Therefore the CI/PI must report any urgent safety measures to the MHRA directly, and in parallel to the Sponsor.

14.12 Notification of Serious Breaches of GCP and/or the protocol

Any Protocol Deviations, Violations, Potential Serious Breaches and Urgent Safety Measures will be recorded using the Sponsor’s Log issued during the Sponsor’s Trial/Site Initiation meeting/visit.

Regulation 29A of the Medicines for Human Use (Clinical Trials) Regulations 2004 [Statutory Instrument 2004/1031], as amended by Statutory Instrument 2006/1928, contains a requirement for the notification of “serious breaches” of GCP or the trial protocol:

(1) The Sponsor of a clinical trial shall notify the licensing authority in writing of any serious breach of:

- (a) The conditions and principles of GCP in connection with that trial; or
- (b) the protocol relating to that trial, as amended from time to time in accordance with regulations 22 to 25, within 7 days of becoming aware of that breach.

(2) For the purposes of this regulation, a “serious breach” is a breach which is likely to effect to a significant degree:

- (a) The safety or physical or mental integrity of the subjects of the trial; or
- (b) The scientific value of the trial.

The Sponsor will be notified immediately of any case where the above definition applies during the trial conduct phase. The Sponsor’s SOP on the Protocol Violation/Deviations and Serious Breaches will be followed.

15 Data management and quality assurance

15.1 Confidentiality

All data will be handled in accordance with the Data Protection Act 1998.

The Case Report Forms (CRFs) will not bear the subject’s name or other personal identifiable data. The subject’s initials, and trial Identification Number (ID), will be used for identification.

